**Table 5: Pre-specified Dose/Schedule Modification for AEs Related to Study Drug**

	Dosage Level(s)	ATG-010 Dose Administered
Starting dose	0	80 mg BIW (total dose: 160 mg per week)
Dose reduction	-1	100 mg QW
	-2	80 mg QW
	-3*	60 mg QW

\* If the Investigator believes further dose reduction could still benefit the patient, a decision can be made through discussion with the Sponsor's Medical Monitor.

**Table 6: Guidelines for Supportive Care and Dose Modification**

**Please pay attention to the following suggestions:**

- For all hematological or non-hematological AEs unrelated to ATG-010, the dose of

ATG-010 may be maintained per the Investigator's discretion after the Sponsor's Medical Monitor is consulted.

- For all AEs related to ATG-010, if stable disease is maintained  $\geq 4$  weeks by the prescribed dose reduction/interruption in Table 6, dose re-escalation may be considered after approval by the Sponsor's Medical Monitor.

Adverse Reaction a	Occurrence, count	Action
Hematological adverse reactions		
Thrombopenia		
Platelets count 25,000 to < 75,000/m 	Any	
 
Lower the dose of ATG-010 by 1 level (see Table 5).
 

Platelets count 25,000 to < 75,000/m  , with concomitant hemorrhage	Any	
 
Interrupt ATG-010.
 
After recovery from hemorrhage, lower the dose by 1 level and re-initiate ATG-010 administration (see Table 5).
 

Platelet count < 25,000/m 	Any	
 
Interrupt ATG-010.
 
Monitor platelet count, until it is restored to a level of at least 50,000/m^3.
 
Lower the dose by 1 level and re-initiate ATG-010 administration (see Table 5).
 

Neutropenia		
Absolute neutrophil count 0.5 to $1.0 \times 10^9/L$ , without fever	Any	
 
Lower the dose of ATG-010 by 1 level (see Table 5).
 

Absolute neutrophil count < $0.5 \times 10^9/L$ or febrile neutropenia	Any	
 
Interrupt ATG-010.
 
Continuously monitoring neutrophil count, until it is restored to <math>\geq 1.0 \times 10^9/L</math>.
 
Lower the dose by 1 level and re-initiate ATG-010 administration (see Table 5).
 

Anaemia		
Hemoglobin < 8.0 g/dL	Any	
 
Lower the dose of ATG-010 by 1 level (see Table 5).
 
Blood transfusion and/or adopting other therapies in clinical guidelines.
 

Life-threatening consequences (urgent intervention indicated)	Any	
 
Interrupt ATG-010.
 
Continuously monitor hemoglobin, until it is restored to a level <math>\geq 8</math> g/dL.
 
Lower the dose by 1 level and re-initiate ATG-010 administration (see Table 5).
 
Blood transfusion and/or adopting other therapies in clinical guidelines.
 

Non-hematological adverse reactions		
Hyponatremia		
Sodium level $\leq 130$ mmol/L	Any	
 
Interrupt ATG-010 and give appropriate supportive care.
 
Continuously monitor sodium level, until it is restored to <math>\geq 130</math> mmol/L.
 
Lower the dose by 1 level and re-initiate ATG-010 administration (see Table 5).
 

Fatigue		
Grade 2 (lasting more than 7 days) or grade 3	Any	
 
Interrupt ATG-010.
 
Continuously monitor, until fatigue is resolved to grade 1 or baseline level.
 
Lower the dose by 1 level and re-initiate ATG-010 administration (see Table 5).
 

Nausea and vomiting		
Grade 1 or 2 nausea (oral intake reduced without manifest body weight loss, dehydration, or malnutrition), or, grade 1 or 2	Any	
 
Continue ATG-010 administration, and initiate additional anti-nausea administration.
 

Adverse Reaction a	Occurrence, count	Action
vomiting (not more than 5 times per day)		
Grade 3 nausea (insufficient oral intake of energy or liquid), or , grade 3 or above vomiting (not less than 6 times per day)	Any	
 
Interrupt ATG-010.
 
Continuously monitor, until nausea or vomiting is resolved to grade 2 or below or baseline level.
 
Initiate additional anti-nausea administration.
 
Lower the dose by 1 level and re-initiate ATG-010 administration (see Table 5).
 

Diarrhea		
Grade 2 (daily defecation increased by 4 to 6 times compared to baseline)	First time	
 
Continue ATG-010 administration, and give supportive care.
 

	Second and subsequent	
 
Lower the dose of ATG-010 by 1 level (see Table 5).
 
Give supportive care.
 

Grade 3 and above (daily defecation increased by 7 or more times compared to baseline; hospitalization indicated)	Any	
 
Interrupt ATG-010 and give supportive care.
 
Continuously monitor, until diarrhea is resolved to grade 2 or below or baseline level.
 
Lower the dose by 1 level and re-initiate ATG-010 administration (see Table 5).
 

Weight loss and anorexia		
Body weight decreased by 10% to < 20%, or , anorexia with manifest weight loss or malnutrition	Any	
 
Interrupt ATG-010 and give supportive care.
 
Continuously monitor body weight, until it is restored to more than 90% of baseline body weight.
 
Lower the dose by 1 level and re-initiate ATG-010 administration (see Table 5).
 

Other non-hematological adverse reactions		
Grade 3 or 4 (life-threatening)	Any	
 
Interrupt ATG-010.
 
Continuously monitor until the reaction is resolved to grade 2 or below, lower the dose by 1 level and re-initiate ATG-010 administration (see Table 5).
 

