### 9.3. Multiple Myeloma Response Criteria

In this study, response is assessed per IMWG criteria (Kumar 2016) All MM assessments must be carried out at each time point specified in this study protocol (Table 1).

Response will be assessed according to IMWG criteria for response assessment in MM (Appendix 3). The response must be confirmed using 2 consecutive samples. The time interval between samples can be discussed with Medical Monitor. Samples can be collected on the same day but must be analyzed independently.

- Complete Response (CR)
- Stringent Complete Response (sCR)
- Very Good Partial Response (VGPR)
- Partial Response (PR)
- Minimal Response (MR)
- Stable Disease (SD)
- Disease progression (PD)

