#### 11.1.4. Dosage Adjustments in Patients with VGPR

In order to improve long-term disease control and tolerability, dose reduction in patients with a very good antitumor activity of ATG-010 is allowed by this study protocol. Therefore, for patients with

≥ VGPR lasting for ≥ 6 months and whom the Investigator believes may benefit from dose reduction, the following dose reductions may be considered after the Sponsor's Medical Monitor is consulted: (a) the dose of dexamethasone may be reduced by 40%, or (b) the dose of ATG-010 may be lowered by 1 level, or (c) the dosing frequency may be reduced to once weekly. Normally, dexamethasone should always be given on the day of ATG-010 dosing. Patients who receive dose reduction according to this protocol should have appropriate MM tumor assessment labs being monitored at least once every 2 weeks (e.g., FLC), so that the dose may be re-escalated to their initial dose when evidence of disease progression appears. These monitoring studies may be done at local laboratories.

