### 11.1.5. Guidelines for Dose Reduction due to Toxicity

Toxicity will be graded according to CTCAE v4.03 criteria; these grades of severity are applicable to the treatment adjustments described below.

If two or more toxicities occur at the same time, dose modification will be determined based on the highest grade of severity.

As described in each section of applicability to the specific toxicities, re-escalation of study drug dose is allowed. If the treatment is delayed by more than 28 days due to drug-related toxicity, patient's study protocol treatment may be canceled.

All dose modifications or treatment delays must be documented in the electronic case reporting form (eCRF) and corresponding reasons must be provided.

According to the observations from the ongoing Phase 1 study in patients with advanced hematologic malignancies and solid tumors, ATG-010 has a very wide therapeutic range with activities from approximately 6 mg/m^2 to ≥60 mg/m^2. Therefore, in order to ensure the best specific anti-tumor activity and tolerability in patients, dose reduction and/or modification of schedule are allowed, as shown in Table 5 and Table 6. Patients should also be actively treated with supportive care to reduce toxicities.

For all grade ≥3 hematological and non-hematological AEs that are unrelated to ATG-010, after discussion with the Sponsor's Medical Monitor and at the discretion of the Investigator, the dose of ATG-010 may be maintained if the patient can continue the oral administration.

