#### 11.1.5.1. ATG-010 Dose Reduction due to Decreased Glomerular Filtration Rate

ATG-010 is not mainly eliminated by kidney; therefore, there is no need to change the dose of ATG-010 in the presence of kidney dysfunction; however, creatinine clearance must be  $>20$  mL/min, otherwise ATG-010 plus low-dose dexamethasone treatment cannot be initiated. If creatinine clearance is decreased during the treatment period and is considered unrelated to ATG-010, the dose of ATG-010 may be maintained, but patient's condition must be closely monitored. If creatinine clearance is decreased to  $< 20$  mL/min, it is considered to be related to ATG-010, and then the dose of ATG-010 should be lowered by 1 level. If creatinine clearance is restored to  $>20$  mL/min and stays at this level for 4 weeks, the dose of ATG-010 can be restored to the previous level. If dialysis is given during the ATG-010 plus low-dose dexamethasone treatment period, ATG-010 plus low-dose dexamethasone must be given after dialysis.

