#### 11.1.5.2. Adjustment of ATG-010 Dose in the Presence of Infection

Any patient with grade  $\geq 3$  infection should interrupt ATG-010, until the infection is clinically resolved or the patient is clinically stable, and then ATG-010 administration can be re-initiated by lowering 1 dose level. If the Investigator assesses that the infection is unrelated to the study drug and decide the administration of study drug can be continued, this decision should be made per discussion with the Sponsor's Medical Monitor.

Dexamethasone should be adjusted according to the guidelines of the medical institution, with

adrenal suppression being taken into account. Missed doses shall not be made up. While re-initiating ATG-010 regimen, patients can continue long-term treatment with antibiotics or other antimicrobial agents per the Investigator's discretion.

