### **12.1.1. Follow-up of AE and SAE**

All AEs occurring during the study period should be followed up according to the Good Clinical Practice, until the events are resolved, stabilized, or judged as no longer clinically significant, or until the patient is medically stable or the event is a chronic disease. Any AE assessed as study drug-related must be followed up until it is resolved or stabilized.

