### Appendix 3. International Myeloma Working Group Response Criteria, Myeloma

**Table 10: International Myeloma Working Group Response Criteria (Kumar 2016)**

Standard IMWG Response Criteria 	
Response subcategory	Response criteria
Complete Response (CR)	Negative IFE of serum and urine, disappearance of any soft tissue plasmacytomas (SPD), and <5% plasma cells in bone marrow aspirates
Stringent Complete Response (sCR)	CR as defined above plus normal FLC ratio  and absence of clonal cells in bone marrow biopsy by immunohistochemistry ( $\kappa/\lambda$ ratio $\leq 4:1$ or $\geq 1:2$ for $\kappa$ and $\lambda$ patients, respectively, after counting $\geq 100$ plasma cells  )
Very Good Partial Response (VGPR)	Serum and urine M-protein detectable by IFE but not on electrophoresis, or $\geq 90\%$ reduction in serum M-protein plus urine M-protein level $<100$ mg per 24 hours
Partial Response (PR)	$\geq 50\%$ reduction of serum M-protein plus reduction in 24-hour urine M-protein by $\geq 90\%$ or to $<200$ mg per 24 hours. If the serum and urine M-protein are unmeasurable, a $\geq 50\%$ decrease in the difference between involved and uninvolved FLC levels is required in place of the M-protein criteria. If serum and urine M-protein are unmeasurable, and serum FLCs are also unmeasurable, $\geq 50\%$ reduction in plasma cells is required in place of M-protein, provided baseline bone marrow plasma cell percentage was $\geq 30\%$ . In addition to the above criteria, if present at baseline, a $\geq 50\%$ reduction in the size (SPD) of soft tissue plasmacytomas is also required 
Minimal Response (MR)	$\geq 25\%$ but $<49\%$ reduction of serum M-protein, and reduction in 24-h urine M-protein by 50-89%. In addition to the above criteria, if present at baseline, a $\geq 50\%$ reduction in the size (SPD) of soft tissue plasmacytomas is also required 
Stable Disease (SD)	Not recommended for use as an indicator of response; stability of disease is best described by providing the TTP estimates. Not meeting criteria for CR, VGPR, PR or progressive disease

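### Outside creatinine clearance, the only stated clinical condition for raising the ATG-010 dose after a related AE is a myeloma response category, not recovery of the AE

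*Combined protocol and SAP*

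**What the plan says.** Section 11.1.5 points to toxicity-specific rules: "As described in each section of applicability to the specific toxicities, re-escalation of study drug dose is allowed". The general instruction that opens Table 6 then sets one condition for every drug-related AE: "For all AEs related to ATG-010, if stable disease is maintained" for at least 4 weeks under the table's reduction or interruption, re-escalation may be considered once the Medical Monitor approves. No AE grade, laboratory value or resolution is named.

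Two other re-escalation rules exist:

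- Section 11.1.4 covers cuts made for a lasting VGPR or better, with monitoring "so that the dose may be re-escalated to their initial dose when evidence of disease progression appears".
- Section 11.1.5.1 covers creatinine clearance. If it returns above 20 mL/min and "stays at this level for 4 weeks, the dose of ATG-010 can be restored to the previous level".

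Section 11.1.5.2 (infection) gives a restart rule one level down but no rule for going back up. Section 11.1.1 sends every dose change through the investigator and the Medical Monitor.

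**The concern.** Stable disease is a response term in this protocol. It is listed among the response categories in section 9.3, it is a component of DCR in section 6.2.2, and Appendix 3, Table 10 defines it as "Not meeting criteria for CR, VGPR, PR or progressive disease". A patient can hold that category for 4 weeks whatever has happened to the toxicity. A patient whose toxicity has cleared but who is in PR or better does not hold it.

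At stake are dosing safety and consistency between sites. When the dose goes back up after a related AE, the written condition concerns the myeloma and gives neither the site nor the Medical Monitor a toxicity level to apply.

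**Working it through.** No formula in the plan applies here; the check is a reading of the text with a row count.

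**1. Wording used for a patient's condition.** Where the English text means that a patient has settled, it uses other words. Section 11.1.5.2 says "until the infection is clinically resolved or the patient is clinically stable" and section 12.1.1 says "until the patient is medically stable or the event is a chronic disease". The words in the Table 6 instruction match the response category instead.

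**2. Rows of Table 6.** Two rows continue the dose, 4 reduce it without interruption, and 10 interrupt it and restart one level lower: 2 + 4 + 10 = 16. Rows that lower the dose: 4 + 10 = 14. Rows that state when the dose may rise: 0. So the pointer in section 11.1.5 to toxicity-specific rules finds only the creatinine clearance rule, and the other related AEs depend on the general instruction.

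**3. Can the restart levels stand in?** They apply to restarting at the lower dose, and the 4 reduction-only rows have none. Each of the 10 was set against the reduction and interruption triggers:

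| Interruption row | Restart condition | Overlap with a trigger |
|---|---|---|
| Platelets 25,000 to <75,000 with hemorrhage | hemorrhage over; no platelet level | 25,000 to <75,000 |
| Platelets <25,000 | at least 50,000 | 50,000 to <75,000 |
| Grade 3 or higher diarrhea | Grade 2 or below, or baseline | second or later Grade 2 episode |
| Weight loss or anorexia | weight above 90% of baseline | anorexia with malnutrition at such a weight |
| ANC <0.5 or febrile neutropenia | at least 1.0 | the value 1.0 |
| Sodium 130 or lower | at least 130 | the value 130 |
| Life-threatening anemia | hemoglobin at least 8 g/dL | none |
| Fatigue | Grade 1 or baseline | none |
| Grade 3 nausea, or Grade 3 or higher vomiting | Grade 2 or below, or baseline | none |
| Other non-hematological, Grade 3 or 4 | Grade 2 or below | none |

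Overlaps: 2 (platelet ranges) + 1 (diarrhea) + 1 (anorexia) + 2 (single values) = 6 of 10; the other 4 have none. Patients whose own baseline already lies inside a row are not counted.

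**4. Size of one step up (Table 5, weekly dose).** Level -1 to 0: 160/100 = 1.60, or +60%. Level -2 to -1: 100/80 = 1.25, or +25%. Level -3 to -2: 80/60 = 1.33, or +33%.

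**5. Where the gap bites.** While a patient still meets a reducing row, that row's instruction stands. The gap therefore lies mainly with an AE that persists below every trigger, or that has only just dropped below one. In both cases 4 weeks of stable disease satisfies the written condition, and nothing asks how long the toxicity has been settled.

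**The case against.** The context points to toxicity. The sentence opens with drug-related AEs and speaks of stability reached through a dose reduction or interruption, which would settle a toxicity rather than a myeloma. The creatinine clearance rule has the same shape: reduce, recover, hold for 4 weeks, restore. The document is a translation. It is therefore quite possible that a stabilised AE was meant, and a reader who infers that the sponsor deliberately chose a response criterion goes further than the documents allow. What stands is that the English text says otherwise and gives no recovery level under either reading.

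The rule is also permissive, comes under a heading of suggestions and needs the Medical Monitor's approval. A reader might take a patient at level -1 with platelets of 60,000 and 4 weeks of stable disease as being told to raise and lower the dose at once. That is too strong: a permission does not override the standing instruction to reduce at that count. The safeguard limits the risk but supplies no criterion.

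Finally, if a myeloma condition was intended, leaving out deep responders could be deliberate, since section 11.1.4 favours less drug after a lasting VGPR. A reader might infer that one correction suits both readings. It does not: replacing the phrase would then remove an efficacy condition, so any such condition has to be written separately.

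**Conclusion.** The point holds as a defect in an operative dosing rule that should be corrected. Outside creatinine clearance, the only stated clinical condition for raising the dose after a related AE is a myeloma response category; no row of Table 6 and no approval step adds a recovery criterion, and 6 of the 10 restart conditions overlap a trigger.

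Confidence is moderate, for two reasons: the text is a translation, and the text of footnote a on the Table 6 header is missing from the copy examined, so it could bear on the point.

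The documents do not support reading this as an instruction to re-escalate patients with active toxicity, or as a threat to the primary result. The ORR test, the sample size of 82 and the 80% power do not depend on it. Nor do the documents allow an estimate of how many patients would be affected.

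**What to change.** Replace the sentence in the Table 6 general instruction with:

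> After any ATG-010-related AE, re-escalation may be considered, subject to the Medical Monitor's approval, if the AE that led to the reduction or interruption has recovered so that it no longer meets any Table 6 criterion for dose reduction or interruption (or has returned to baseline), and this has been maintained for at least 4 weeks on the reduced dose.

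This follows the pattern of section 11.1.5.1, which stays unchanged. If the sponsor also intended a myeloma condition, add it as a separate requirement of no disease progression.

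The baseline alternative matters for patients enrolled under inclusion criterion 9c with platelets of 50,000 to <75,000, whose starting count already lies in the reduction row.

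A requirement of Grade 1 or less is not proposed: Table 6 accepts Grade 2 as recovery for nausea and vomiting, diarrhea and other non-hematological AEs, and nothing in the documents supports a stricter level. A lasting Grade 2 event of that kind therefore remains a judgement for the Medical Monitor.

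Cost: a one-sentence amendment, with written IRB/EC approval before use (section 14.5). Some patients may be re-escalated later. No visits are added for platelets or ANC: hematology is already weekly in Cycles 1 and 2 and on Day 1 of each later cycle (Table 1).

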### 8.2. Inclusion Criteria

Patients must meet all of the following inclusion criteria to be eligible to enroll in this study:

1. Aware and sign the informed consent form (ICF) voluntarily.
2. Age  $\geq 18$  years.
3. Patients with multiple myeloma must have previously received regimens with immunomodulatory agent (lenalidomide) and proteasome inhibitor (bortezomib), are refractory to both drugs, and are refractory or intolerant to the most recent line of therapy (Patients documented as intolerant are allowed to be screened only after discussing and obtaining an approval from Sponsor Medical Monitor). Refractory MM includes primary refractory (patients do not achieve minimal response (MR) or have disease progression during therapy) or secondary refractory patients have progression within 60 days after completion of therapy).
4. Any non-hematological toxicities (except for peripheral neuropathy as described in exclusion criterion #17) that are relevant to previous therapies must have resolved to  $\leq$  Grade 2 prior to the first dose of study drug.
5. Adequate hepatic function: total bilirubin  $<2 \times$  upper limit of normal (ULN) (for patients with Gilbert's syndrome, a total bilirubin of  $<3 \times$  ULN is required), AST  $<2.5 \times$  ULN, and ALT  $<2.5 \times$  ULN.
6. Adequate renal function: estimated creatinine clearance  $\geq 20$  mL/min (calculated using the formula of Cockroft-Gault).
7. Eastern Cooperative Oncology Group (ECOG) Performance Status of 0, 1, or 2.
8. Measurable MM as defined by at least one of the following:
  - a. Serum M-protein (by serum protein electrophoresis, SPEP)  $\geq 5$  g/L,
  - b. 24 hours-Urinary M-protein excretion  $\geq 0.2$  g (200 mg),
  - c. Serum free light chain (FLC)  $\geq 100$  mg/L with abnormal FLC ratio.
9. Adequate hematopoietic function (no platelet transfusions within 1 week, and no red blood cell transfusions within 2 weeks prior to screening examination):
  - a. Hemoglobin level  $\geq 80$  g/L
  - b. ANC  $\geq 1000/\text{mm}^3$  ( $1.0 \times 10^9/\text{L}$ )
  - c. Percentage of plasma cells in bone marrow  $<50\%$ , platelet count  $\geq 75,000/\text{mm}^3$  ( $75 \times 10^9/\text{L}$ ); or percentage of plasma cells in bone marrow  $\geq 50\%$ , platelet count  $\geq 50,000/\text{mm}^3$  ( $50 \times 10^9/\text{L}$ ).
10. Female patients of childbearing potential must meet below two criteria:

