#### **11.1.5.3. Cases not Requiring ATG-010 Dose Reduction**

Below are exceptional cases to the dose modification guidelines. There is no need to interrupt ATG-010 in the following cases:

- Any grade of alopecia
- Electrolyte or serum analyte (e.g., urate) abnormalities that can be reversed by standard intervention

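### Table 6 both interrupts and restarts ATG-010 at a sodium of exactly 130 mmol/L (minor; a one-symbol correction)

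*Combined protocol and SAP*

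**What the plan says.** All references are to the protocol.

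- **Table 6, Hyponatremia.** One row, for any occurrence. At sodium ≤130 mmol/L the first action is "Interrupt ATG-010 and give appropriate supportive care". The second is "Continuously monitor sodium level, until it is restored to" ≥130 mmol/L. The third is to resume one dose level lower.
- **Section 11.1.5.3.** It opens "Below are exceptional cases to the dose modification guidelines" and says no interruption is needed for electrolyte or serum-analyte "abnormalities that can be reversed by standard intervention". The hyponatremia row does not point to it.
- **Section 11.1.1.** Every dose change goes to the Investigator and the Medical Monitor before it is made. Table 6 presents its contents as suggestions.
- **Table 6, Neutropenia.** The first row, "Absolute neutrophil count 0.5 to" 1.0 × 10^9/L without fever, lowers the dose one level. The second row, for counts below 0.5 or febrile neutropenia, interrupts and says "Continuously monitoring neutrophil count, until it is restored to" ≥1.0 × 10^9/L, then restarts one level lower.
- **Table 5.** Weekly ATG-010 doses at levels 0, −1, −2 and −3 are 160, 100, 80 and 60 mg.

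**The concern.** A stop rule and its restart rule should not both be true of the same result. In the sodium row they share the value 130. A reading of 130 that causes an interruption already satisfies the condition for ending it. A patient whose sodium has climbed back to 130 may be restarted at a value that the same row treats as a reason to stop.

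Two sites could therefore act differently on the same result. One restarts at 130 while the other waits for a higher value. After a restart at 130, one site sees a recovered patient and another sees a fresh trigger. What is at stake is consistent dosing under a safety rule. The analyses touched are the dose-modification summaries and the optional exploratory look at dose modification and efficacy in Section 13.1.5.

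**Working it through.** The plan states no figure on this point, so the check is of the logic of the limits.

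**Sodium as written.** Stop if Na ≤ 130; restart if Na ≥ 130.

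| Sodium (mmol/L) | Stop condition | Restart condition |
|---|---|---|
| 129 | met | not met |
| 130 | met | met |
| 131 | not met | met |

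The overlap of (≤130) and (≥130) is {130}.

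**Does other text settle 130?** Section 11.1.5.3 turns on whether the abnormality can be corrected, not on its value. It removes some patients from the row but gives no rule for those who remain. Section 11.1.1 names who decides but gives no criterion.

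**How wide is one value?** The documents do not give the reporting precision, so this is an assumption. If sodium is reported in whole mmol/L, 130 stands for 129.5 to <130.5, a width of 1 mmol/L. If it is reported to one decimal, the width is 0.1 mmol/L.

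**Dose involved.** Once a patient at level 0 has been interrupted, the row itself prescribes the step from 160 to 100 mg/week, so that step is not in dispute. The overlap leaves open when to restart. On a literal reading it also leaves open whether a repeat value of 130 after restart triggers another step: 100 − 80 = 20 mg/week, and 20/100 = 20% of the level −1 dose.

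**Neutropenia, for comparison.** The reduction row is 0.5 to 1.0 and the restart rule is ≥1.0. The first limit is read as inclusive, because Table 6 marks exclusive upper limits elsewhere with <, as in the platelet row. The overlap is {1.0}. Unlike sodium, the two conditions sit in different rows. The restart rule applies only to a patient already interrupted for a count below 0.5 or for febrile neutropenia. The rows therefore meet only when such a patient restarts at exactly 1.0.

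**After the edits.** For sodium, (≤130) and (>130) have no common value and leave no gap. For ANC, (<0.5), (0.5 to <1.0) and (≥1.0) likewise have no common value and no gap.

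**The case against.** The best defense is that the rules are sequential: the stop rule is for patients on drug and the restart rule for patients off drug, so only one is consulted at a time. This settles the order of reading but does not remove the overlap. In the sodium row, the result that stops treatment also counts as recovery, and a restart at 130 is at once within the stop range.

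Second, Section 11.1.5.3 takes correctable electrolyte disturbances out of the row. This narrows the point and stands to that extent. It sets no limit for the cases left in the row, and a reader of Table 6 is not sent to it.

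Third, no dose change is automatic. The Medical Monitor is a sponsor role common to all sites, which limits differences between sites. That also stands, but a decision-maker who turns to the table at 130 still finds both instructions.

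Fourth, the consequence is small. Only one value is involved, the number of patients is unknown, and the primary safety analysis in Section 13.3.6 uses the original dose level. This is correct and is why the point is rated minor.

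**Conclusion.** The sodium point holds as a minor drafting fault: one row gives opposite instructions at exactly 130 mmol/L, and nothing elsewhere in the protocol resolves that value. The ANC overlap is of the same type but smaller, and it rests on reading 1.0 as inside the reduction row. The number of patients affected cannot be derived.

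A reader might infer more, in four ways that the documents do not support.

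- **A contested 37.5% cut at ANC 1.0.** For a patient on treatment at 1.0, only the reduction row applies. The step from 160 to 100 mg/week (60/160 = 37.5%) is a clear instruction. Inclusion criterion 9b accepts 1.0 at entry, but entry limits are not matched to reduction limits here: 9c admits some patients with platelets from 50,000, while the first platelet row reduces below 75,000.
- **A contradiction for platelets.** Restart is allowed at 50,000, inside the row "Platelets count 25,000 to < 75,000". The natural reading is that the platelet rows are alternative actions for one event, so one reduction. The footnote to the table's first column header is not in the text available, and Section 5.1 ties reductions to a package insert that is also unavailable. Either may settle the matter, so no gap is shown.
- **A pattern across toxicities.** The diarrhea rows take the same form as platelets and show no more. The weight-loss row is not a clean comparator, because it can also be triggered by anorexia with weight loss or malnutrition and no 10% threshold.
- **An effect on the primary result.** The sample size and the ORR test (15% against 28%, 82 patients) use nothing from Table 6. No effect on ORR, alpha or power is claimed.

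**What to change.** 1. **Hyponatremia row.** Keep interruption at ≤130 mmol/L, change the restart condition to >130 mmol/L, and add a reference to Section 11.1.5.3.
2. **Neutropenia, first row.** Write 0.5 to <1.0 × 10^9/L.

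The cost is wording in one table and a note to sites, with no added patients or scheduled visits.

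The sodium edit has a downside: a patient at exactly 130 waits for a later result above 130, possibly with one more test. The wait counts toward the 28-day limit on drug-related delay. Past that limit, Section 11.1.5 says treatment may be ended, while the synopsis (Study Drug, Dose and Administration) says the patient is to be withdrawn from study treatment. From Cycle 3, Table 1 schedules serum chemistry only on Day 1 of each cycle, 4 × 7 = 28 days apart. Sites should therefore not wait for the scheduled test, and the row's call for ongoing monitoring already implies an earlier one.

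Interrupting at <130 and restarting at ≥130 would also remove the overlap and avoid the wait. It would, however, relax the stop limit by leaving a patient at exactly 130 on drug, so keeping the stop limit is the more cautious choice.

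The ANC edit also changes a clear instruction: a patient on treatment at exactly 1.0 would no longer be reduced, and at level 0 would stay at 160 instead of 100 mg/week. The sponsor should accept that knowingly.
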